Subjects with a history of bipolar disorder will be excluded from the study. At this time, tDCS has never been reported to cause a seizure in any patient population. Seizures are, however, theoretically possible and a seizure plan is in place for such an unlikely event. Importantly, the majority of the above side effects have been also reported in association with sham (fake) tDCS, even with similar rates. The table below comes from a recent review of tDCS safety and shows the percentage of studies reporting these common sensations (Brunoni et al., 2011) These data suggest that other factors may cause these sensations, such as your expectations or the pressure of head straps or caps.

**Table 3.** Frequency of adverse effects in 117 (active group) and 82 (sham group) experiments. We considered the presence of adverse effect if the study reported its occurrence in at least one patient

Sensation	Active group	Sham group
Itching	46 (39.3%)	27 (32.9%)
Tingling	26 (22.2%)	15 (18.3%)
Headache	17 (14.8%)	13 (16.2%)
Burning	10 (8.7%)	8 (10%)
Discomfort	12 (10.4%)	11 (13.4%)
Total	117 studies	82 studies

Due to the investigational study, there may be risks, side effects that are not yet

nature of this discomforts or known.

We will follow current safety guidelines for tDCS and will use a current strength of up to 2mA and a duration of up to 20 minutes. Few, if any, side effects are reported with these parameters (Nitsche & Paulus, 2011). We will also monitor subjects for discomfort during and after each session. During the session, we will verbally ask the subject if they are experiencing discomfort. The Speech-Language Pathologists will be in the room while the stimulation is being applied and will consequently be available to assist the patients in communicating any side effects they may be experiencing. After the sessions, subjects will complete the following post-tDCS questionnaire:

tDCS Adverse Effects Questionnaire – Session \_\_\_\_\_

---

Do you experience any of the following symptoms or side-effects?	Enter a value (1–4) in the space below (1, absent; 2, mild; 3, moderate; 4, severe)	If present: Is this related to tDCS? (1, none; 2, remote; 3, possible; 4, probable; 5, definite)	Notes
Headache			
Neck pain			
Scalp pain			
Tingling			
Itching			
Burning sensation			
Skin redness			
Sleepiness			
Trouble concentrating			
Acute mood change			
Others (specify)			

---

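### The only itemised symptom form is completed after sessions with no record of symptoms on arrival, and nausea, visual sensation and shock-like sensation have no named line on it

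*Combined protocol and SAP*

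**What the plan says.** The Risks text of the tDCS section states the monitoring window: "We will also monitor subjects for discomfort during and after each session". It names these sources of information.

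- **In session, a verbal question:** "During the session, we will verbally ask the subject if they are experiencing discomfort". The plan does not say that the answer is written down.
- **In session, a clinician present:** "The Speech-Language Pathologists will be in the room while the stimulation is being applied". The same sentence adds that they can help subjects communicate side effects of any kind.
- **After the session, a form:** "After the sessions, subjects will complete the following post-tDCS questionnaire". It has a blank for the session number and asks "Do you experience any of the following symptoms or side-effects". Severity is graded "1, absent; 2, mild; 3, moderate; 4, severe". If a symptom is present, a second column asks "Is this related to tDCS? (1, none; 2, remote; 3, possible; 4, probable; 5, definite", and a third is for notes. There are ten named lines and one open line for anything else.

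Section 5-1.5 (Methodology) adds a numeric scale with faces, placed in front of the client to signal discomfort or a wish to stop. The Data Monitoring section provides a yearly review that includes adverse events, by someone outside the study. Section 5-1.6 (Statistical Design) plans comparisons of language performance and describes no analysis of adverse effects.

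**The concern.** The form records a level at one time point. A headache that came in with the subject and one that began under stimulation get the same severity grade. The design offers no other way to separate them. All subjects receive active tDCS, so there is no sham arm, and the 300 earlier subjects in section 5-1.6 are described as a therapy comparison with no mention of symptom data. The plan itself accepts that "other factors may cause these sensations, such as your expectations or the pressure of head straps or caps".

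The form also does not fully match the plan's own risk list. An effect without a named line is recorded on the form only if the subject raises it and it is written on the open line. According to the Participants section every subject has aphasia, so an unprompted free-text entry is a weak route here.

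At stake is the quality of the safety record: how far it can show which symptoms appeared or worsened with stimulation, and whether effects the plan already expects are asked about.

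**Working it through.** The plan states no figure to reproduce. The check is a comparison of the risk list with the form.

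**Step 1: timing.** The protocol was searched for a symptom rating before stimulation, an onset or change-from-arrival field, and a stated recall period. None is described. The verbal question and the faces scale both concern discomfort only, and neither is given a pre-session time.

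**Step 2: which lines are affected.** The ten named lines are headache, neck pain, scalp pain, tingling, itching, burning sensation, skin redness, sleepiness, trouble concentrating and acute mood change.

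- Five can plausibly be present on arrival: headache, neck pain, scalp pain, sleepiness, trouble concentrating.
- Four describe the electrode site (tingling, itching, burning, redness), where a pre-session level matters little.
- One, acute mood change, already asks about change.

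So 5 + 4 + 1 = 10, and the ambiguity concerns mainly the first five. Section 5-1.5 describes about 14 + 6 + 5 = 25 hours of therapy a week, so arriving tired is plausible. The documents give no per-session background rate, and none is estimated here.

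**Step 3: risk list against form.** The bulleted list under Risks has 4 effects under the electrode, 1 only during stimulation, 4 during or after, and 5 rare: 4 + 1 + 4 + 5 = 14.

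| Coverage on the form | Effects |
|---|---|
| Named line | tingling, itching, burning sensation, skin redness, headache, mood change |
| No named line on any reading | nausea, visual sensation, shock-like sensation |
| At most partly covered | discomfort, fatigue, nervousness, memory or other cognition, skin burn |

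That is 6 + 3 + 5 = 14. The boundary of the last row is a judgement. Discomfort may be partly caught by scalp or neck pain, fatigue by sleepiness, nervousness by mood change, cognition by trouble concentrating, and skin burn by burning sensation and redness. A stricter reader would move some of these into the row above. The firm part is the three effects with no line.

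**Step 4: when those effects occur.** The plan places visual sensation only during stimulation and the shock-like sensation at its start. A form completed later, in the present tense and with no stated window, is poorly placed to pick up either. The in-session question asks only about discomfort.

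**Step 5: volume.** The Parameters text gives 15 to 30 sessions. At one form per session, as the session-number blank implies, that is 15 to 30 post-session forms and 0 pre-session ratings per subject.

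**The case against.** The case on the other side is substantial.

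- **Attribution is already asked for.** Each symptom marked present gets a five-level relatedness grade starting at none, and there is room for notes. A subject who arrived with a headache can say so. This stands as partial mitigation. It remains an after-the-fact judgement with no recorded earlier level, so it does not establish whether a symptom was new or worse.
- **Help is in the room.** The Speech-Language Pathologist can help a subject communicate any side effect during stimulation, including a visual or shock-like one. This also stands. It is support for communication, not a recorded prompt.
- **The form may be meant to cover the whole session.** The risk text says sensations under the electrode usually stop soon after stimulation begins, yet tingling and itching are on the form. That is a fair inference, and it is why the window should be written down.
- **Little depends on it.** No adverse-event analysis is planned, and an independent yearly review exists. This sets the weight of the point.

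A reader might infer more: that nothing on the form can be attributed, that the unlisted effects cannot be recorded at all, or that a fixed fraction of listed effects is missed. The documents support none of these. Electrode-site lines hardly need a baseline and mood is asked as a change. The open line allows any effect to be entered. The fraction depends on how loosely the lines are matched.

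**Conclusion.** The point holds in a limited form. For symptoms that can be present on arrival, the post-session severity entries do not show whether the symptom was new or worse, and nothing else in the plan records an earlier level. Nausea, visual sensation and shock-like sensation have no named line, and five further listed effects are at most partly covered.

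This is a modest, inexpensive improvement to data collection. It does not affect the language outcomes, and no misattribution rate can be given because the documents supply no background rate. The conclusion assumes that the form as printed is complete and that no separate recording procedure exists outside the protocol. If the form feeds the yearly review, which the plan does not state, that review is where the gain would be seen.

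**What to change.** 1. **Form.** Add fixed lines for nausea, nervousness, fatigue and skin burn. State the time window, for example during or since stimulation.
2. **In-session question.** Extend it from discomfort to visual and shock-like sensations, and record the answer.
3. **Symptoms on arrival.** For the few symptoms that can be present beforehand, either take a short pre-session level on the same 1-4 scale, or add a field to the existing form asking whether the symptom was present before today's session and, if so, whether it is the same or worse. Where mood and nervousness are compared, rate each as a current level at both times; comparing two ratings of change would not be informative. Leave electrode-site lines as post-session only.
4. **Reporting.** Report all post-session ratings and, separately, symptoms that were new or worse.

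**Cost.** Items 1 and 2 need one revised form and a short written answer. For item 3, the extra field adds little. A pre-session rating is more debatable. At an assumed 2 to 5 minutes with clinician help (not a figure from the documents), it takes 15 x 2 = 30 to 30 x 5 = 150 minutes per subject. Against about 4 x 14 = 56 hours of individual therapy, that is 0.5/56 = 0.9% to 2.5/56 = 4.5%. Against a stimulation period of up to 20 minutes, it is 2/20 = 10% to 5/20 = 25% per session, which favours the extra field or a very short list.

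Asking beforehand may also slightly raise symptom expectation. None of this replaces a sham comparison: effects of therapy, expectation and head straps would remain in the new-or-worse counts, and the report should say so.

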### **tDCS**

Parameters: All subjects will receive up to 30 sessions of active tDCS. Depending on the availability of the subject, the session number may vary from 15 to 30 sessions. Each session will begin with up to 20 minutes of active tDCS at 2mA in conjunction with the individual behavioral therapy. The anode electrode will be placed over the left hemisphere and the reference electrode will be placed on the contralateral frontopolar cortex. The specific montage will be determined based on individual patient characteristics.

Risks: tDCS is generally considered safe with no more than minimum risk. In a meta-analysis of over 200 tDCS studies conducted from 1998 to 2010, 56% of studies mentioned adverse events (Brunoni et al., 2011). The available evidence suggests that it is safe. However, it is investigational in nature, which means that we are doing these studies to learn more about tDCS. The most common side effects associated with tDCS based on the available scientific data are:

Sensations under the electrode: These sensations usually stop shortly after tDCS begins but can sometimes continue throughout and for a brief period after tDCS.

- Mild tingling • Light itching • Slight burning sensation • Discomfort

Effects reported that occur ONLY during tDCS:

- Visual sensation during switching on and off the stimulation

Other effects that can occur both during and after tDCS include:

- Fatigue,
- Skin redness
- Headache
- Changes in concentration, memory, or other cognitive abilities. This is partially what we will be testing.

Additionally the following rare side effects have been described in previous studies that used tDCS:

- Nausea
- Nervousness
- It is also possible that the electric current can cause a burn on your skin. This is unlikely because we are using a smaller dose than what is known to cause burns and because we use saline or gel to reduce electrical resistance that leads to burns.
- A shock-like sensation at the initiation of tDCS was reported in one participant.
- Changes in the activity of the prefrontal region (front of the head) have the potential to induce sudden changes in your mood. Hypomania has been reported in a few patients receiving tDCS for bipolar disorder and depression but never in normal controls.

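### The post-session adverse-effects form gives no recall period, so brief electrode sensations (three of its ten named items) may be under-recorded, by an amount that cannot be calculated

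*Combined protocol and SAP*

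**What the plan says.** All of the following is in the tDCS section of the protocol unless another section is named.

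- **When the form is given.** "After the sessions, subjects will complete the following post-tDCS questionnaire". The interval since the current stopped is not stated.
- **What it asks.** "Do you experience any of the following symptoms or side-effects". Each line is coded from 1 for absent to 4 for severe, and a second column asks about relatedness to tDCS for symptoms that are present. There is a notes column, but no field for onset, duration or resolution.
- **When stimulation occurs.** "Each session will begin with up to 20 minutes of active tDCS".
- **Time course of sensations under the electrode.** The list reads "Mild tingling • Light itching • Slight burning sensation • Discomfort", and the text says: "These sensations usually stop shortly after tDCS begins but can sometimes continue throughout and for a brief period after tDCS".
- **Effects with a longer window.** A separate list (fatigue, skin redness, headache, cognitive changes) opens with "Other effects that can occur both during and after tDCS include".
- **Checks during stimulation.** "During the session, we will verbally ask the subject if they are experiencing discomfort". Speech-language pathologists are present to help subjects report side effects, and section 5-1.5 puts a 1-to-10 scale with faces within the client's view.

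**The concern.** The form and the protocol's account of the side effects do not fit together. The sensations listed first among the most common effects are described as short-lived, yet the instrument meant to capture them is given after the session and uses the present tense. A subject whose burning sensation has gone, and who answers literally, enters absent.

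The quality of the safety record is at stake, not the language results. Each subject has 15 to 30 sessions, so any loss recurs each time. An effect that has ended and goes unreported can only lower the recorded frequency, so the bias runs towards better tolerability. The Data Monitoring section provides for a yearly look at adverse events, and that review could inherit the understatement. If some subjects answer for now and others for the session, the recorded frequencies also have no single meaning.

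**Working it through.** The plan states no adverse-effect rate for its own subjects, so there is no figure to reproduce. The check is a count of the form's lines and a comparison of the passages.

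**1. Count of items by stated time course.** The form has ten named lines plus an open line for others.

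| Time course given in the Risks text | Lines on the form | Count |
|---|---|---|
| Usually ends early | Tingling, itching, burning sensation | 3 |
| Can occur during and after | Headache, skin redness, trouble concentrating, sleepiness (if read as fatigue) | 4 |
| None stated | Neck pain, scalp pain, acute mood change | 3 |

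3 + 4 + 3 = 10. The problem attaches to the first row. Discomfort, the fourth electrode sensation, has no line of its own. Nor has the visual sensation at switching on and off, so question tense is not the main issue for that effect.

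**2. Order of events.** Stimulation opens the session and lasts up to 20 minutes; the form follows the session. A sensation that fades soon after onset has gone by the time the form is given, however short the gap after the current stops. A sensation that lasts throughout, or briefly beyond, may or may not still be there, depending on a gap that the protocol does not give.

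**3. Size.** Let *f* be the share of episodes that have ended when the form is filled in, and *r* the share of answers given for the present moment. If *r* does not depend on whether the sensation has ended, and nothing else prompts a report:

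share missed = *r* × *f*

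- If every subject answers for the session, *r* = 0 and the share missed is 0 × *f* = 0.
- If every subject answers for now, *r* = 1 and the share missed is 1 × *f* = *f*.

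The word for how often these sensations end early suggests *f* above 50% but gives no number, and nothing in the documents fixes *r*. The share missed therefore lies anywhere from 0 to 100%.

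**4. Could the published table supply a rate?** No. It counts experiments in which at least one patient had the effect (for itching, 46/117 = 39.3% in the active group). That is not a per-subject or per-session frequency.

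**5. Do in-session reports fill the gap?** The verbal question, the faces scale and the pathologists' help all operate while the sensation is present. The protocol does not say that any of these reports is written down or carried onto the form.

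**6. Severity.** Even if a subject answers for the whole session, the form does not say whether the code means the worst, the typical or the final level.

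**The case against.** The strongest reply is that the form need not be read as a question about this instant. It carries a session number, is introduced as a post-tDCS questionnaire and asks about relatedness to tDCS, all of which invite an answer for the session. The severity codes do not say that they describe the current state. The in-session question is put in the continuous present, and the form's question is not. This stands, and it rules out the stronger conclusion that a reader might draw: that most of these effects will be recorded as absent, or that recorded rates will fall below half the true ones. That would need every subject to answer for now, together with a persistence rate and an interval that the documents do not give. The ambiguity remains a weakness, because the Participants section admits only people with aphasia and includes receptive aphasia.

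Second, the protocol allows that these sensations can last throughout and for a short time afterwards, and a post-session form suits the four items that can occur later. This also stands, and it confines the point to three lines.

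Third, several people and aids are on hand during stimulation, and the form has a notes column and an open line. This is fair as regards immediate safety. It does not settle the record, because no transfer is described.

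Fourth, sections 5-1.2 and 5-1.6 concern language outcomes and subject characteristics; no adverse-effect rate is a planned outcome, and the yearly review is not said to tabulate the form. The sensations are also described as slight. This limits the consequence without removing it.

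**Conclusion.** The point holds in a limited form. The form has no recall period and no worst-level instruction, it follows stimulation given at the start of the session, and recording of in-session reports is not described. Tingling, itching and burning, three of the ten named items, may therefore be under-recorded, and subjects may differ in the period for which they answer.

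The direction, towards better apparent tolerability, follows if at least some subjects answer for the present moment and their in-session reports do not reach the form. The amount cannot be calculated. The documents do not support a claim that most such effects will be lost, nor any specific recorded rate. The language outcomes are unaffected. The change is still worth making because it is small and improves the only itemised safety record.

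**What to change.** In the questionnaire in the tDCS section:

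1. Reword the question to: *At any time during or since today's stimulation, did you have any of the following?*
2. Define the severity code as the worst level reached in that period.
3. Add a yes/no column: *Still present now?*
4. State that what the subject reports during stimulation (verbal question, faces scale, or with the pathologist's help) is entered on the same form.

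The cost is one reworded question, a line defining the code, one added column, and the small effort of writing down in-session answers. The downside is that the transient-sensation items on forms already completed cannot be pooled with those on the new form. Any summary should show the two versions separately for tingling, itching and burning.

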**Data Monitoring**

Once a year, a review of participant recruitment procedures and consent forms as well as any adverse events will be conducted by a member of [name] research team, who is not part of this study.
